In summary, SNRB, despite utilized frequently in the diagnostic work-up with patients with lumbar radiculopathy, vary widely in their sensitivity and specificity. The reasons, as outlined above, are multifactorial. The proposed study aims to minimize the known limitations of these injections and prospectively define their positive and negative predictive value in a homogenous group of patients undergoing surgery for lumbar foraminal stenosis and radiculopathy. The design will define a threshold of response utilizing both subjective and objective measures and more accurately predict excellent results following surgery.

Scientific Approach

Patients, age 18-80, who present with unilateral lower extremity radiculopathy due to degenerative foraminal stenosis will be considered for this study. Patients will be included if they present with radiculopathy and with imaging and/or clinical history or physical exam that does not demonstrate a clear neurogenic source of their pain. Examples include MRI with multi-level foraminal stenosis or discordance between MRI and clinical radiculopathy. All patients enrolled in the study will undergo a SNRB of the suspected symptomatic nerve root. Patients will undergo lumbar foraminotomy regardless of the response to the injection.

Patients will be excluded if there is a clear correlation between imaging and radiculopathy. An example would be an L5 radiculopathy in the face of an acute L4/5 herniated disc. Additional exclusion criteria include: radiculopathy associated with trauma, tumor or infection. Non-radicular lower extremity pain will also be excluded. Patients who cannot tolerate the SNRB without IV sedation will not be enrolled.

Subjects must be available for the entire study duration (12 months) and willing and able to comply with scheduled visits including completing pain diary and all patient reported outcome questionnaires.

Patients will be contacted by phone during the study follow-up (48 hours post injection).

Other exclusion criteria:

Surgery requiring multi-level decompression and/or fusion

Surgical indication for malignancy, injection or acute or emergency trauma

History of major surgery within 3 months prior to enrollment

Pregnant females

Presence of severe acute, chronic medical or psychiatric condition

Patients meeting inclusion criteria and following signing of the informed consent will undergo SNRB prior to surgery. **The surgeon will be blinded to the**

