To improve the diagnostic value of SNRB, a threshold between positive and negative responses will be set that is best able to predict whether a patient will have a good surgical outcome. To measure the response to injection, post-injection VAS pain scores and functional assessments will be compared to pre-injection values for each patient.

First, the functional and VAS pain measures of improvement will be analyzed individually. A positive functional response to injection will be defined by setting thresholds in the timed 30-meter walk test that best differentiates patients who respond to surgery from those who do not. The accuracy of the test will be defined by its sensitivity and specificity and by its negative and positive predictive values. Separately, a threshold defining a positive response to injection will be set using VAS leg pain improvements over pre-injection values.

Then, a logistic regression analysis will be performed, including pain assessments and walk test improvements as predictors. This model will assign a value between 0 and 1 that represents how likely it is that a patient who responds to SNRB with some amount of reduction in leg pain and improvement in

[name]

Threshold Response of Selective Nerve Root Block

functional ability has a good surgical outcome. A threshold in the model's predictive values will be set to define a positive response to the injection. This will again be done to maximize its diagnostic accuracy with respect to sensitivity and specificity and to positive and negative predictive values.

Positive and negative predictive values and their 95% confidence intervals will be reported both for the individual analyses and for the combined logistic regression analysis. Lastly, variable selection will be performed in an attempt to simplify the logistic regression model.

Due to the fact that a threshold response to SNRB has not been studied, we are not able to perform an adequate power analysis. We will use the data from this pilot study to perform a power analysis for a planned larger randomized trial. To have an adequate sample yet complete the study in a 12 month time period we plan to enroll 50 patients.

Plans for Dissemination of Results

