We plan to disseminate the results of this study in multiple venues. First, we will plan to submit the results via abstract for presentation at the Lumbar Spine Research Society Annual Meeting. The results of this study will also be submitted for publication. All presentations and publications will acknowledge the Lumbar Spine Research Society.

The results of this pilot study will be utilized as pilot data for the submission of a larger multicenter prospective trial. When completed the results will also be submitted for presentation at the LSRS annual meeting and for publication. We anticipate multiple publications originating from a larger study. All presentations and publications will acknowledge the Lumbar Spine Research Society.

Future Funding and Next Steps

The preliminary results from this study will be utilized as data for a larger randomized multi-center study. This pilot study data will help formulate a proper power analysis for the design of a larger study. Moreover, the pilot data will permit insight into the threshold effect of SNRB, which can be used in the design phase of a larger study. We plan to submit an NIH RO1 grant in collaboration with other major spine academic centers. With the expenditures on therapeutic and diagnostic injections increasing each year and significant questions regarding their efficacy, we believe the NIH would be very interested in funding such a study.

Following completion of this study, we will first use the data to design a multi-center study. We believe that the data from this study will help us understand the proper SNRB to be performed and define what it truly means to have a "positive" injection. Moreover, we believe our study will define a threshold response for a

[name]

Threshold Response of Selective Nerve Root Block

positive or negative injection. This data will then aid in the design of an appropriate much larger study. Our plan is to collaborate with our peers at large interdisciplinary spine centers in conducting a multi-center prospective study.

Bibliography:

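### Cut-offs for a positive block are set whether or not block response is associated with surgical outcome, and the analysis names no benchmark that would reveal a null result

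*Combined protocol and SAP*

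**What the plan says.** Statistical Analysis opens by promising that "a threshold between positive and negative responses will be set that is best able to predict whether a patient will have a good surgical outcome". It then works in stages. For function, a positive response comes from "setting thresholds in the timed 30-meter walk test that best differentiates patients who respond to surgery from those who do not". A VAS leg-pain cut-off is set separately. A logistic model combines the pain and walk measures, and "A threshold in the model's predictive values will be set to define a positive response to the injection", again so as to maximise diagnostic accuracy. PPV and NPV are reported with 95% confidence intervals, for the single measures and for the model. Variable selection comes last, to simplify the model.

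No step is conditional. The document gives no test of association, no minimum AUC or accuracy, no comparison of PPV with the overall success rate, and no wording for the case where no usable threshold is found.

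On sample size the section states that "we are not able to perform an adequate power analysis" and then: "To have an adequate sample yet complete the study in a 12 month time period we plan to enroll 50 patients".

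Other sections expect a threshold to emerge. The summary closing Background and significance says "The design will define a threshold of response utilizing both subjective and objective measures", and Future Funding and Next Steps says "we believe our study will define a threshold response". The latter section adds that the pilot's threshold data may inform the design of a larger study.

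**The concern.** Specific Aims and Hypothesis asks whether any degree or length of response to the block predicts an excellent surgical result. That question can be answered no. The analysis goes straight to the best cut-off and never sets the result against what a block carrying no information would give. Searching for the best cut-off in the same patients who are then used to describe its accuracy makes some apparent accuracy almost certain.

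At stake is how a null or weak result would read. Every patient has surgery whatever the block shows, so the data could reveal an uninformative block. Without a benchmark, such a block would appear in the report as a defined threshold with better-than-chance accuracy, and that figure would be available to those designing the next study. This is separate from optimism in the estimates: shrinking a PPV for optimism does not by itself tell the reader whether association was shown.

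**Working it through.** **Inputs from the document.** 50 patients; three sets of cut-offs (walk, VAS, model); PPV and NPV with 95% intervals. No alpha, effect size or expected success rate is given, so the figure of 50 cannot be reproduced from a calculation.

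**Assumptions.** Success rate 50 to 80%; cut-off chosen by the Youden index J = sensitivity + specificity − 1 (the plan names no single index); exact (Clopper-Pearson) intervals treating the cut-off as fixed in advance; 40 evaluable patients as a dropout case.

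**1. No-information values.** If block response is independent of outcome and the success rate is p, then at any cut-off sensitivity = 1 − specificity. So J = 0, PPV = p and NPV = 1 − p.

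**2. Why the base rate matters, from the document's own background.** In the retrospective series of 100 consecutive patients, 41 of 51 block-positive patients did well. Of nine block-negative patients, six did well, two did not and one was lost. The quoted sensitivity of 85.4% is 41/48, which counts the lost patient as a success.
- Success rate on that basis: 48/60 = 80.0%, against a PPV of 41/51 = 80.4%.
- Failure rate: 12/60 = 20.0%, against an NPV of 2/9 = 22.2%.
- J = 0.854 + 0.167 − 1 = 0.021.

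A PPV of 80.4% looks strong until it is set beside 80.0%. With only nine block-negative patients this is an illustration, not evidence about the present trial.

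**3. Null simulation, 50 patients.** Integer VAS change and continuous walk change, neither related to outcome; success 50, 70 or 80%; 1,500 trials per setting.

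| Rule | Apparent J above 0 | Mean apparent J (truth 0) | PPV or NPV interval wholly above no-information value |
|---|---|---|---|
| VAS alone | 93–95% | 0.12–0.16 | 7–9% |
| Walk alone | 98% | 0.16–0.20 | 12–15% |
| Logistic, both | 100% | 0.27–0.35 | 35–38% |

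At a 70% success rate the logistic rule gave, on average, PPV 0.83 (no-information value 0.70) and NPV 0.48 (no-information value 0.30). Further runs with two normal measures correlated 0.4 and success of 50, 65 or 80% gave mean J of 0.27 to 0.35, and 34–40% in the last column. With 40 evaluable patients the logistic mean J was 0.30 to 0.39.

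**4. What a test against no association would show.** In the same null settings, a 5% likelihood-ratio test of the two-measure model against the intercept-only model rejected in about 5–7% of trials. A permutation test of the maximised J (VAS) rejected in 3.0–4.3%. An unadjusted Fisher test at the selected logistic cut-off rejected in 43–47%, so testing at the chosen cut-off is no substitute.

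**5. What 50 patients can show.** For one measure, the standard error of the AUC under no association is √[(n₁ + n₀ + 1)/(12 n₁ n₀)].
- 25 successes, 25 failures: √(51/7500) = 0.0825. The observed AUC must exceed 0.5 + 1.96 × 0.0825 = 0.662.
- 40 successes, 10 failures: √(51/4800) = 0.1031. It must exceed 0.5 + 1.96 × 0.1031 = 0.702.

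For the joint test of two measures, the share of trials non-significant when association is real:
- AUC 0.70 for each, 50 patients: about 20–40%.
- AUC 0.70 for each, 40 evaluable: about 30–51%.
- AUC 0.65 for each: about 48–65%.

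These figures are for two measures; adding duration of relief would change them.

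**The case against.** A reader might infer that the plan can only answer yes. The document does not support that. Accuracy is itself the reported result, Aim 1 is estimation of PPV and NPV, and a poor threshold can be reported as poor. In most null trials the planned intervals would not sit wholly above the no-information value. What remains is that no reference value is named, and that intervals ignoring the cut-off search mislead in about a third or more of null trials for the combined model.

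That the logistic rule shows J above 0 in every null trial is close to automatic, because the cut-off is chosen in-sample to maximise it; this does not show that the investigators would claim prediction. The model may also fit either sign: in about 81% of simulated null fits at least one measure had a negative coefficient, so that more improvement predicted a worse result. A reader could notice this, but the plan does not ask for the direction to be checked. The informative figures are the size of the apparent J and the behaviour of the intervals.

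A reader might also infer that the cut-off will be carried into the next trial. The text says only that the data can inform its design. The statement that "we believe our study will define a threshold response" is an expectation in a funding section, not an analysis rule.

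Finally, a hard significance gate is debatable in a self-declared pilot. A joint likelihood-ratio test is non-directional, would cover three different thresholds at once, and would often miss a real effect. A test on VAS and walk change alone would also omit duration, which Aim 2 requires. These objections stand, and they shape the fix.

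**Conclusion.** The point holds in a limited form. Cut-offs are set unconditionally in the same 50 patients, and nothing in the plan separates a cut-off that reflects prediction from one that reflects the search. For a block unrelated to outcome, the combined rule would show a mean apparent Youden index of about 0.27 to 0.35. The planned intervals would falsely suggest information in about 34–40% of trials for the model and about 7–15% for single measures. They are a partial safeguard.

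The sizes rest on assumed success rates of 50–80%, the Youden index, simulated marker distributions and intervals that treat the cut-off as fixed; the pattern did not change across the settings tried. There are trivial exceptions where no cut-off exists, such as nearly identical outcomes or a model that does not converge. Pilot status explains the missing power calculation, but not the missing benchmark. The point is worth correcting before analysis; it does not undermine the design or the data collection.

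**What to change.** Amend Statistical Analysis as follows.

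1. Name the block-response predictors before analysis, including VAS leg-pain change, 30-meter walk change and duration of relief (Aim 2), and say which pain assessment supplies the VAS change.
2. For each measure, report the AUC with a 95% confidence interval against 0.5, in the direction that more improvement predicts a better outcome. Test the full logistic model, before variable selection, against the intercept-only model by permuting the outcome or by likelihood ratio. Report the signs of the coefficients, because the joint test ignores direction.
3. Report each PPV beside the overall success rate and each NPV beside the overall failure rate.
4. Add wording such as: 'If association is not shown, the corresponding cut-off will be reported as exploratory and descriptive only, and the result will be worded as prediction not shown, not as absence of prediction.' Let each AUC govern the wording for its own measure and the joint test the wording for the combined model.

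The cost is a few sentences and a few extra analyses of data already collected; no patients or visits are added. The drawback is low power: with 50 patients or fewer the result will often be inconclusive. The test should therefore decide how a threshold is described and should not suppress the estimates, which the larger trial's planners will still want to see.

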Aim 1: Prospectively determine the positive and negative predictive value of SNRB in the surgical treatment of lumbar foraminal stenosis. Prior to a single level foraminotomy for lumbar foraminal stenosis patients will undergo SNRB of the suspected nerve root. All enrolled patients will proceed to surgery despite the response to injection. All injections will be performed in a standard format-utilizing anesthetic only and under fluoroscopic guidance. All patients will complete an ambulation assessment immediately before and following the injection. Distance and time will be recorded. All injection patients will be called within 48 hours of the injection to determine response to the injection and recorded as Pre- and Post injection VAS leg as well as length of time of the response recorded in minutes. Patients will be seen at 6 weeks, 3 months and 12 months following surgery and outcome measured by VAS-leg, Oswestry Disability Index (ODI), Pain Disability Questionnaire (PDQ) and EQ-5D.

Aim 2: Determine the threshold of positive predictive response. The relationship between degree of pain improvement following SNRB and outcomes following surgery is currently unknown. Each patient will therefore report their change in leg pain before and after injection as well as the length of time of improvement. These data will be used to determine the optimal improvement in leg pain and duration of improvement, which predicts a statistical and meaningful improvement in leg pain following foramintomy.

Background and significance

Lumbar radiculopathy in the setting of degenerative disease is a common presenting symptom; its prevalence is estimated to be 2-5% of the US population. Although patients typically present with pain associated with one or multiple nerve roots, their MRI may demonstrate multi-level foraminal and/or

canal stenosis. Moreover, these degenerative findings seen on imaging are common in asymptomatic people. Several studies have found no correlation between MRI findings and clinical symptoms^{4, 16, 17, 25}. Others have shown that MRI evidence of stenosis increases with age despite absence of symptoms, noting that almost 20% of individuals >60 years of age and up to 80% of those >70 years of age have evidence of stenosis without clinical symptoms^{3, 20}.

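### Cut-offs are tuned and their PPV/NPV reported in the same 50 patients, with no internal validation and no uncertainty for the cut-offs, so the figures carried to the next trial are optimistic

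*Combined protocol and SAP*

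**What the plan says.** The Statistical Analysis section describes three data-driven rules in one cohort with a planned enrolment of 50.

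- Walk test: a positive response is defined by "setting thresholds in the timed 30-meter walk test that best differentiates patients who respond to surgery from those who do not".
- VAS leg pain: a threshold is set separately from the improvement over pre-injection values.
- Logistic model, "including pain assessments and walk test improvements as predictors": a threshold is placed on the predicted probability, and "This will again be done to maximize its diagnostic accuracy with respect to sensitivity and specificity and to positive and negative predictive values".

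On reporting: "Positive and negative predictive values and their 95% confidence intervals will be reported both for the individual analyses and for the combined logistic regression analysis". The final modelling step is: "Lastly, variable selection will be performed in an attempt to simplify the logistic regression model".

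Aim 2 (Specific Aims and Hypothesis) makes the cut-off itself a result: "These data will be used to determine the optimal improvement in leg pain and duration of improvement". The results are then carried forward. Statistical Analysis states "We will use the data from this pilot study to perform a power analysis for a planned larger randomized trial", and Plans for Dissemination of Results states "The results of this study will also be submitted for publication". Future Funding and Next Steps adds that what is learned about the threshold may be used when the larger study is designed.

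No section mentions a hold-out sample, cross-validation, bootstrap, shrinkage or optimism correction. No section gives an interval for a cut-off or says that the larger study will validate it.

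**The concern.** A cut-off chosen because it separates good from poor outcomes in a given sample partly fits the noise in that sample. Accuracy computed in the same patients is therefore too high on average, and more so when a model is fitted first. The planned confidence intervals treat the cut-off as if it had been fixed in advance, so they do not allow for the search.

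Three gaps add to this. Sensitivity, specificity, PPV and NPV trade off, so an instruction to maximise all four does not determine a cut-off. The model's predictors are not listed. Only PPV and NPV receive intervals, so a reader cannot tell how firmly the data locate the threshold.

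Both main deliverables are affected: PPV and NPV answer Aim 1, and the cut-off answers Aim 2. An optimistic PPV used in the next trial's power calculation could make that trial too small.

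**Working it through.** **The plan's own figures.** The 50 patients have no power or precision basis; the number was set by what can be enrolled in 12 months, so there is no calculation to reproduce. The only accuracy figures that can be checked are those of the retrospective series of 100 consecutive patients described in Background and significance: PPV 41/51 = 80.4%, NPV 2/9 = 22.2%, sensitivity 41/48 = 85.4%, specificity 2/12 = 16.7%. All four match if the patient lost to follow-up is counted as a good outcome. That series also supports a good-outcome rate near 80%: (41 + 6)/59 = 79.7%.

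**Inputs.** From the plan: n = 50, cut-offs chosen and assessed in the same patients. Assumed, because the plan does not give them: Youden cut-off; 50% or 80% good outcomes; normally distributed measures, either useless or 0.8 SD better in good-outcome patients; correlation 0.5 between two measures. Two predictors (one pain, one walk) is the smallest reading of the model.

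**Reference value.** With a 0.8 SD difference the best cut-off is the midpoint, 0.4 SD. Sensitivity and specificity there are both Φ(0.4) = 0.655. PPV is therefore 65.5% at 50% good outcomes, and 0.8 × 0.655 / (0.8 × 0.655 + 0.2 × 0.345) = 88% at 80%. No rule built on this one measure can have a higher Youden index.

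**Optimism, one measure (mean PPV).**

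| Good outcomes | Measure | Apparent | True |
|---|---|---|---|
| 50% | useless | 63% | 50% |
| 50% | 0.8 SD | 73% | 66% |
| 80% | useless | 89% | 80% |
| 80% | 0.8 SD | 93% | 88% |

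**Apparent minus true, in points, over the four settings.**

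| Rule | PPV | NPV | Coverage of exact 95% CI |
|---|---|---|---|
| One measure | 4 to 13 | 7 to 13 | 91–97% |
| One coarse measure (0.4 SD steps) | 3.5 to 11 | 5 to 12 | not tabulated |
| Two predictors | 6 to 16 | 8 to 17 | 92–93% with signal, 79–84% useless |
| Two predictors, backward selection | 6 to 16 | 9 to 17 | 90–93% with signal, 80–88% useless |

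A separate simulation with four predictors, at most one of them informative, and good-outcome rates of 50% to 80% gave PPV inflated by about 8 to 19 points, NPV by about 13 to 22, and coverage of 62–83%.

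**Spread of the cut-off (one measure, 0.8 SD signal).** The middle 95% of chosen cut-offs ran from −0.5 to 1.3 SD at 50% good outcomes (width 1.8) and from −0.8 to 1.4 SD at 80% (width 2.2). Both exceed twice the 0.8 SD gap between the groups. If the SD of VAS change is 2 to 3 points on a 0–10 scale (assumption), the spread is 2 × 1.8 = 3.6 to 3 × 2.2 = 6.6 points. The two-predictor probability cut-off ran from 0.30 to 0.71 at 50% good outcomes.

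**Possible effect on the next trial (illustrative design).** Test PPV = p against 50%, two-sided 5%, 80% power:

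n = [(1.96 × 0.5 + 0.842 × √(p(1 − p))) / (p − 0.5)]²

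- Apparent, p = 0.728: n = 35.3, so 36 block-positive patients.
- Bootstrap-corrected, p = 0.684: n = 55.5, so 56.
- True, p = 0.658: n = 76.2, so 77.

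True power is Φ[(0.158√n − 0.98)/√(0.658 × 0.342)]. It is Φ(−0.07) = 47% with 36 patients and Φ(0.43) = 67% with 56.

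**Does the remedy work?** A bootstrap that repeats the whole procedure moved PPV at 50% good outcomes with signal from 73% to 68% (true 66%) for one measure, and from 75% to 69% (true 67%) for two predictors. Across settings, 1 to 7 points of optimism remained. The bootstrap 2.5–97.5% range of the single-measure cut-off contained the best cut-off in 96% of runs (50% good) and 92% (80% good).

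**The case against.** This is a pilot. Its results are called preliminary, the plan hopes only for insight into the threshold, and a larger study is intended to follow. Confidence intervals are planned, and for a single measure their coverage stays near nominal. Every magnitude above rests on inputs that the documents do not give. The power illustration is a single-group test, whereas the next study is described as randomized, with no endpoint or comparator stated. Sampling noise also matters: in the one-measure case with signal at 50% good outcomes, the error of apparent PPV averaged +7 points with an SD of 9, and apparent PPV fell below the true value in 23% of runs. Any point estimate from 50 patients is thus a fragile basis for power. Finally, variable selection comes after the PPV/NPV reporting, so accuracy of the simplified model may not be a planned output.

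Much of this stands as qualification. Pilot status limits the severity. The failure of coverage belongs to the combined model, mainly when the predictors carry no information. The next trial could be undersized, but the documents do not show by how much, and the selection figures apply only if that model's accuracy is reported.

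The core is not removed. Near-nominal coverage does not take the bias out of the point estimate, which is what a power calculation uses. The direction was the same in every setting tried, including 30% good outcomes (apparent PPV 54% against true 46%). Nothing in the plan assigns validation of the cut-off to the later study.

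**Conclusion.** The concern holds and should be fixed before analysis. Followed as written, the plan gives PPV and NPV that are too favourable on average and a cut-off with no statement of its precision. Under the stated assumptions the inflation is roughly 4 to 16 points for PPV and 7 to 17 for NPV with one or two continuous predictors, slightly less for a coarse scale, and more if more predictors enter. The combined model is worst affected, because its intervals can also under-cover. For single measures the planned intervals are adequate, but the point estimates and the cut-off are not. The size depends on the assumed criterion, outcome rate, signal strength and number of predictors. The number analysed may also fall below 50, since patients without an adequate injection are excluded (Description of Procedures).

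**What to change.** In Statistical Analysis:

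1. Name one cut-off criterion in advance, for example Youden's J, for the individual and combined analyses, and list the model's predictors.
2. Repeat the whole procedure (model fit, any variable selection, cut-off choice) in at least 200 bootstrap samples. State how separation is handled, for example Firth's penalised likelihood in every fit, dropping resamples with fewer than two patients in either outcome group.
3. Report optimism-corrected sensitivity, specificity, PPV and NPV as the main estimates, with the uncorrected values and their intervals beside them labelled as apparent. State that the correction is partial and that the apparent intervals ignore the tuning, which matters mainly for the combined model. Do not use plain percentile bootstrap intervals for PPV and NPV: with two predictors their coverage was 38–86%. A Wilson interval centred on the corrected value (87–96%) is an option.
4. Report the 2.5–97.5% bootstrap range of each cut-off, and label the cut-offs exploratory pending validation in the larger study.
5. Use the corrected PPV and NPV in that study's power analysis, with lower values as a sensitivity check; given the sampling noise, that check may matter as much as the correction.

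The cost is a few sentences and a little more code, with no new data or patients. The price is less favourable figures, and about 1 to 7 points of optimism would remain on the simulations above.
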